5.9. Safety Analysis

5.9.1. Extent of Exposure

All patients who receive at least 1 dose of abemaciclib (i.e. the safety analysis set population) will be evaluated for safety and toxicity and exposure.

For abemaciclib, extent of exposure will be measured by pill counts and summarized by cumulatively. The summary will include the total dosages taken and dose intensities. Dose intensity will be calculated as the ratio of total dose taken to the assigned cumulative dose. The assigned cumulative dose for each patient during each cycle is 150 mg per dose \times 2 doses per day \times 21 days = 6300 mg. The assigned cumulative dose while in this study is 150 mg per dose \times 2 doses per day \times number of days on treatment.

The number of cycles received, dose omissions, dose reductions, dose delays, and dose intensity will be summarized for all treated patients by treatment arm based on data from the first 3 cycles as well as based on data from entire treatment period (i.e. first 3 cycles plus extension phase) separately.

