7.1. Treatments Administered

Abemaciclib monotherapy will be administered 200 mg PO BID with specific administration conditions. Patients will be instructed to take their daily doses of abemaciclib either with a meal, without a meal in a modified fasting state (defined as at least 1 hour prior to or 2 hours after a meal), or without regard to food for the first 3 cycles. Patients will be requested to record the abemaciclib dosing and administration conditions followed in a diary. Abemaciclib will be taken on Days 1 to 28 of a 28-day cycle for each treatment arm. [Table JPCP.7.1](#) shows the treatment regimens.

Patients will be instructed to commence loperamide at the first sign of loose stools and thereafter as per local label. See [Section 7.7.1.1](#) for supportive management guidance. Patients will be required to record loperamide dose and frequency in a diary. Loperamide will be supplied or reimbursed by the sponsor according to local laws. If additional antidiarrheals are prescribed by the physician, they should be entered on the concomitant medication CRF.

Table JPCP.7.1. Treatment Administration

Study Arm	Drug	Dose, mg	Route of Administration	Dose Frequency	Administration Conditions
1	Abemaciclib	200	Oral	BID	Take with a meal
2	Abemaciclib	200	Oral	BID	Take without a meal; at least 1 hour before or 2 hours after a meal (modified fasted condition)
3	Abemaciclib	200	Oral	BID	Take without regard to food

Abbreviation: BID = twice a day.

The investigator or his/her designee is responsible for the following:

- explaining the correct use of the drug and planned duration of each individual's treatment to the patient/study-site personnel/legal representative.
- verifying that instructions are followed properly the first 3 cycles. Abemaciclib is taken as per the assigned study arm outlined in [Table JPCP.7.1](#).
- maintaining accurate records of abemaciclib dispensing and collection.
- returning all unused medication to Lilly, or its designee at the end of the study, unless the site is authorized by Lilly or its designee to destroy unused medication, as allowed by local law.
- educating the patient on the management of diarrhea as per [Section 7.7.1.1](#).

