7.2.1. Selection and Timing of Doses

During the on-study treatment period (primary outcome phase and extension phase), a delay of study treatment due to holiday, weekend, inclement weather, or other unforeseen circumstances will be permitted for a maximum of 7 consecutive days and not counted as a protocol deviation. In exceptional cases, for planned delays (including, but not limited to vacation or holidays), additional study treatment may be dispensed. In these cases, patients should return to the original visit schedule calculated from Day 1.

For each study arm, abemaciclib will be administered orally at 200 mg BID, with at least 6 hours separating doses on a continuous schedule and as assigned by administration conditions for each study arm. Details on treatment administration are described in Section 7.1. Treatment with abemaciclib will be given until evidence of disease recurrence or other discontinuation criteria are met (see Section 8).

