7.4.1.1. Dose Adjustments of Abemaciclib

Dose adjustments as outlined in Table JPCP.7.3 are allowed. Abemaciclib must be reduced sequentially by 1 dose level.

For patients requiring dose reduction(s), any re-escalation to a prior dose level is permitted only after consultation with the Lilly CRP. After re-escalation, subsequent dose adjustments should be based on the dose of abemaciclib that the patient is currently receiving.

Table JPCP.7.3. Dose Adjustments of Abemaciclib

Dose Adjustment	Oral Dose	Frequency
0	200 mg	Twice daily with at least 6 hours between doses
1	150 mg	Twice daily with at least 6 hours between doses
2	100 mg	Twice daily with at least 6 hours between doses
3	50 mg	Twice daily with at least 6 hours between doses

If a patient receiving the 50-mg BID dose of abemaciclib requires further dose reduction, the patient must be discontinued from study treatment.

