10.3.3.3. Treatment Compliance

The number of cycles received, dose omissions, dose reductions, dose delays, and dose intensity for the first 3 cycles will be summarized for all treated patients by treatment arm.

Study treatment compliance will be assessed as the proportion of treatment that is actually taken, relative to what is expected, after accounting for protocol-defined dose adjustments. Study treatment taken will be derived from the difference between the total number of tablets/capsules dispensed and returned over the course of the first 3 cycles.

Compliance to the administration condition will be assessed as the proportion of doses during the first 3 cycles of treatment that are taken during the meal window allowed by the assigned administration condition. For each dose of abemaciclib taken during the first 3 cycles, the patient will record the administration condition in a diary.

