5.5. Treatment Compliance

Treatment compliance information for study drug will be collected through capsule counts at each visit. The estimate of percent abemaciclib treatment compliance will be given by:

$$\text{Percent Treatment Compliance} = \frac{\text{actual cumulative dose taken}}{\text{expected cumulative dose to be taken}} \times 100$$

The actual cumulative dose taken will be determined based on counting the number of capsules returned at each visit and subtracting that number from the number of capsules dispensed over the course of the first 3 cycles. The expected cumulative dose to be taken will be determined based on the assigned dose and taking into account any dose reductions or omissions.

Compliance to the administration condition for Arm 1 and Arm 2 will be assessed as the proportion of doses during the first 3 cycles of treatment that are taken during the meal window allowed by the assigned administration condition.

The allowed meal window for Arm 1 (taken with a meal) would be taking abemaciclib during a meal or within 30 minutes of end of meal.

The allowed meal window for Arm 2 (taken without a meal) would be taking abemaciclib greater than 60 minutes before start of meal or taking abemaciclib greater than 120 minutes after end of meal.

There is no window for Arm 3 as the abemaciclib is taken without regard to food.

For each dose of abemaciclib taken during the first 3 cycles, the patient will record the administration condition in a diary. The compliance to the administration condition will be based on the available data obtained from diary.

Compliance with Morning Dose Diary, Evening Dose Diary and Bowel Movements Diary will be calculated as the proportion of the actual number of diaries and expected number of diaries.

In addition, timing of dose administration condition with respect to food intake timing may be summarized by study arms for morning and evening dose separately based on ed diary.

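### SAP 5.9.1 computes dose intensity against 150 mg (and 21 days per cycle), but the protocol assigns 200 mg twice daily for 28 days

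*SAP*

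**What the plan says.** SAP 5.9.1 divides the dose a patient took by the dose assigned. Exposure is to be "measured by pill counts and summarized by cumulatively". Two versions of the assigned dose follow:

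- Per cycle: "The assigned cumulative dose for each patient during each cycle is 150 mg per dose", times 2 doses a day, times 21 days, with 6,300 mg given as the product.
- Whole study: "The assigned cumulative dose while in this study is 150 mg per dose", times 2 doses a day, times the days on treatment.

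The section asks for dose intensity by arm over the first 3 cycles and, separately, over the whole treatment period including the extension. It does not say which formula serves which summary.

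The protocol differs on both inputs. Section 7.2.1: "For each study arm, abemaciclib will be administered orally at 200 mg BID". Section 7.1: "Abemaciclib will be taken on Days 1 to 28 of a 28-day cycle for each treatment arm". In Table JPCP.7.3 (Section 7.4.1.1), 200 mg is level 0 and 150 mg is level 1, the first step down.

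The table itself is a protocol requirement. Section 10.3.3.3: "The number of cycles received, dose omissions, dose reductions, dose delays, and dose intensity for the first 3 cycles will be summarized", by arm, for all treated patients.

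**The concern.** The multiplication in SAP 5.9.1 is correct, but its inputs are not this trial's. No arm starts at 150 mg, no arm has a 21-day cycle, and neither document explains either value. The dose is wrong in both formulas; the cycle length is wrong in the per-cycle one.

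This is a tolerability study concerned with dose lost to diarrhea. A denominator set at the first reduction level makes that loss look smaller than it is: a patient treated at the reduced dose throughout appears fully dosed, and a fully dosed patient appears overdosed. The absolute percentages would be wrong in every arm.

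**Working it through.** **Inputs.** SAP 5.9.1: 150 mg, 2 doses a day, and either 21 days per cycle or days on treatment. Protocol 7.1 and 7.2.1: 200 mg, 2 doses a day, 28 dosing days per 28-day cycle.

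**The SAP's own figure.** 150 × 2 × 21 = 6,300 mg. This matches the printed value, so the text was not damaged in conversion.

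**The protocol's figure.** 200 × 2 × 28 = 11,200 mg per cycle.

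**Inflation** = correct denominator ÷ SAP denominator.

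- Days-on-treatment formula: (200 × 2 × days) / (150 × 2 × days) = 200/150 = 1.333.
- Per-cycle formula, full cycle: 11,200/6,300 = 1.778.

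**Denominators over 3 full cycles (84 days).** Protocol: 3 × 11,200 = 33,600 mg. SAP by days: 150 × 2 × 84 = 25,200 mg. SAP by cycle: 3 × 6,300 = 18,900 mg.

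**What a patient on a constant dose would show over one full 28-day cycle:**

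| Dose, twice daily | Taken (mg) | Correct (÷ 11,200) | SAP, days (÷ 8,400) | SAP, per cycle (÷ 6,300) |
|---|---|---|---|---|
| 200 mg | 11,200 | 100% | 133% | 178% |
| 150 mg | 8,400 | 75% | 100% | 133% |
| 100 mg | 5,600 | 50% | 67% | 89% |
| 50 mg | 2,800 | 25% | 33% | 44% |

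**Break-even for printing 100%.** 150/200 = 75% of the assigned dose by days on treatment; 6,300/11,200 = 56.25% by cycle.

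**Between arms.** A common factor leaves ratios unchanged but stretches differences. As an illustration with assumed values, true arm means of 90% and 80% times 1.333 print as 120.0% and 106.7%. The gap is 13.3 points instead of 10, and the ratio stays at 1.125.

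**Early stoppers.** The choice of formula matters most here. Ten fully dosed days give 200 × 2 × 10 = 4,000 mg. By days on treatment the SAP yields 4,000/3,000 = 133%; by cycle it yields 4,000/6,300 = 63%. With corrected inputs these become 4,000/4,000 = 100% and 4,000/11,200 = 36%. So correcting the inputs aligns the two formulas for full cycles but not for partial ones.

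**The case against.** Nobody could defend 150 mg or 21 days as intended here, so the case on the other side is about how much it matters.

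Dose intensity is not among the endpoints in Table JPCP.4.1. Protocol 10.3 plans no hypothesis tests. None of the six primary endpoints or two combined endpoints in SAP 5.8 uses this denominator. SAP 5.9.1 also reports total dose taken and separate summaries of reductions, omissions and delays, so a patient reduced to 150 mg is still counted as reduced. Values near 133% would probably be noticed when the tables are reviewed. All of this stands and limits the damage to one descriptive table. It does not make the formula right, and a correction made silently in programming would be an undocumented departure from the approved SAP.

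The 1.778 factor is contingent. Exposure is to be summarized cumulatively, which points to the days-on-treatment formula, and no per-cycle dose-intensity table is specified. The figure to lead with is therefore 1.333.

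The disagreement between the two formulas over a full cycle (8,400 against 6,300 mg) is the 21-day error seen again; with 28 days both give 11,200 mg. What remains is a convention for partial cycles. Neither document says that a patient who stops should be measured against a full cycle, so the 36% above only shows what that convention would imply.

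Percent compliance is defined separately in SAP 5.5: "The expected cumulative dose to be taken will be determined based on the assigned dose and taking into account any dose reductions or omissions". No milligram value is given there, but the protocol's 200 mg is the natural reading, so the 75% per-protocol rule is not affected. Because 150 mg is the only assigned dose stated numerically in the SAP, correcting it also removes the chance of it being carried into that calculation.

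**Conclusion.** The point holds. The dose-intensity denominator in SAP 5.9.1 contradicts the protocol, and following it as written would put false absolute values in a table the protocol requires. It should be corrected because the error is certain and the remedy simple; the primary conclusions are not threatened.

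The inflation is 1.333-fold by days on treatment, the likely formula for a cumulative summary, and 1.778-fold per full cycle if the fixed per-cycle figure is used. These sizes assume that the SAP is programmed literally. The statement that ratios between arms survive also assumes that one formula is applied to all arms.

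**What to change.** In SAP 5.9.1, replace 150 mg with 200 mg in both formulas. In the per-cycle formula, also replace 21 days with 28 and the product with 200 × 2 × 28 = 11,200 mg. The days-on-treatment definition can otherwise stay. Add one sentence stating which formula applies to the first-3-cycles summary and which to the entire treatment period; this also settles how partial cycles are handled.

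The cost is a short SAP edit and the matching programming change. Pill counts are already collected, so nothing changes for patients, sites or data capture.

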5.9.2. Adverse Events

All patients who receive at least 1 dose of abemaciclib (i.e. the safety analysis set population) will be evaluated for safety and toxicity.

Primary analysis of adverse events will be performed based on data from the first 3 cycles. The secondary analyses of the adverse events will be done based on data from entire study period.

The Medical Dictionary for Regulatory Activities (MedDRA) Version 21.0 (or higher) will be used to map reported AEs to MedDRA terms. The MedDRA Lower Level Term (LLT) will be used in the treatment emergent computation. Treatment-emergent adverse events (TEAEs) will be summarized by System Organ Class (SOC) and by decreasing frequency of Preferred Term (PT) within the SOC. Preferred terms identified by Medical as clinically identical or synonymous will be grouped together under a single consolidated PT. For example, 'Neutropenia' and 'Neutrophil count decreased' will be reported as 'Neutropenia'. All listings and summaries will use the PT resulting from this process. The National Cancer Institute (NCI) Common Terminology Criteria for Adverse Events (CTCAE) v 4.0 will serve as the reference document for grading the severity of all AEs and other symptoms. Preexisting conditions are defined as AEs that begin prior to the first dose of study drug.

A treatment-emergent adverse event (TEAE) is defined as an event that first occurred or worsened in severity after baseline.

A serious adverse event (SAE) is any AE during this study that results in one of the following outcomes:

- death
- initial or prolonged inpatient hospitalization
- a life-threatening experience (that is, immediate risk of dying)
- persistent or significant disability/incapacity
- congenital anomaly/birth defect
- considered significant by the investigator for any other reason.

Important medical events that may not result in death, be life-threatening, or require hospitalization may be considered SAEs when, based on appropriate medical judgment, they may jeopardize the patient and may require medical or surgical intervention to prevent one of the outcomes listed in this definition above.

Safety analyses will include summaries of the following by treatment arm:

- treatment-emergent adverse events, including severity and possible relationship to abemaciclib
- serious adverse events, including possible relationship to abemaciclib
- treatment-emergent adverse events leading to dose adjustments
- discontinuations from study treatment due to AEs or death
- Maximum Post Baseline Treatment Emergent CTCAE Lab Toxicities
- treatment-emergent abnormal changes in vital signs.

5.9.3. Deaths

All deaths in this study that are not attributed to study disease by the investigator will be listed along with the reason for death, if known. For those deaths attributed to an AE, the listing will include the PT of the AE. A summary of deaths including reasons for death will be produced.

In addition, a listing of all deaths including those due to study disease along with reason for death (if known) will be produced.

5.9.4. Clinical Laboratory Evaluation

A patient listing of all abnormal laboratory data will be provided with a flag for values outside of the laboratory normal range as well as investigator site, patient identifier, age, gender, race, weight, and visit. Abnormal results will be listed separately for the safety population. In addition, the treatment emergent laboratory events will be summarized in table.

In addition to the investigator-reported AEs, all relevant hematology and chemistry laboratory values will be graded according to CTCAE version 4.0. These derived values will be included on the listings of laboratory data.

5.9.5. Vital Signs, Physical Examinations, and other Observations Related to the Study

All vital signs including blood pressure and heart rate will be listed for all enrolled patients.

5.10. Other Analyses

5.10.1. Pharmacokinetic/Pharmacodynamic Analyses

Abemaciclib PK analyses will be conducted on all patients who have received at least 1 dose of study treatment and have had samples collected (see PK sampling schedule in Appendix 4 of the protocol). Pharmacokinetic (PK) analyses will be performed according to a separate PK/PD analysis plan.

5.10.2. Additional Reports to Support Clinical Trial Registry (CTR) Reporting Results

Analyses provided for the Clinical Trial Registry (CTR) requirements include the following:

- Summary of AEs, provided as a dataset which will be converted to an XML file. Both SAEs and ‘Other’ AEs will be summarized by treatment group and by MedDRA PT.
- An AE is considered ‘Serious’ whether or not it is a TEAE.
- An AE is considered in the ‘Other’ category if it is both a TEAE and is not serious.
- For each SAE and ‘Other’ AE, for each term and treatment group, the following are provided:
 - the number of participants at risk of an event (if certain subjects cannot be at risk for some reason, for example, gender-specific AEs, then the study team must adjust the number to only include the patients at risk)
 - the number of participants who experienced each event term
 - the number of events experienced.
- Consistent with www.ClinicalTrials.gov requirements, a threshold for frequency of ‘Other’ AEs can be implemented rather than presenting all ‘Other’ AEs. For example, ‘Other’ AEs that occur in fewer than 5% of patients in any treatment group may not be included if a 5% threshold is chosen. The frequency threshold must be less than or equal to the allowed maximum of 5%.
- The completers in the study is defined as the subjects who have completed three cycles of the study treatment.

6. References

National Cancer Institute. Cancer Therapy Evaluation Program, Common Terminology Criteria for Adverse Events, Version 4.0, DCTD, NCI, NIH, DHHS. 2009.

Leo Document ID = 0021d666-32e5-4c11-bf34-d7a654e83fc4

Approver: PPD

Approval Date & Time: 08-Nov-2018 19:49:49 GMT

Signature meaning: Approved
